5.3.5 Post treatment evaluations

4 weeks after treatment discontinuation (\pm 1 week), patients will have repeat viral load, lymphocyte sub set analysis, immune activation parameters, safety labs including LFTs and creatinine phosphokinase. All visits will be completed on the indicated days of the protocol, for unforeseeable circumstances that might render the patient unable to complete the study visit on the designated days the patient may reschedule within a 2-5 day window except for the end of study visit which may be completed within a 1 week window.

5.4 Subjects can be discontinued from the study for the following reasons:

- Failure to comply with the protocol
- If they develop a serious adverse event (SAE)
- Pregnancy, if a patient becomes pregnant on study; she will stop the study drug and be followed as part of the study through the pregnancy including the peri-partum period to ensure her safety.
- **Any subject with a creatinine phosphokinase (CPK) value greater than 10 times the upper limit of normal (i.e grade 3 or higher), will undergo repeat testing. Repeat testing will be conducted at protocol specified time points (i.e. within 1-3 days of the initial result and also at day 7). Persistently elevated laboratory values, i.e. CPK measurements that remain at the same level or are higher than the initial value, on three consecutive determinations, despite cessation of exercise will result in study drug discontinuation.**
- **In addition, all CPK elevations associated with grade 3 or higher symptoms or for significant symptoms or elevations in CPK that do not fall into either of the above mentioned categories; a conference call with representatives from all three participating sites (either the PI or their designee) will be initiated. Decisions regarding study drug discontinuation for patients meeting the above listed criteria will be made on an individual case by case basis. The medical monitor at the sites will be involved in all decisions regarding study drug discontinuation.**

- Patient develops liver function elevations 3 times the upper limit of normal
- If the serum LDL cholesterol falls to less than 40mg/dl
- Develops a grade 2 or greater allergic reaction to the medicine or develops signs and symptoms of an immediate hypersensitivity reaction to the medication
- Patient needs to start antiretroviral agents using current DHHS guidelines as recommendations.
- Patient develops any condition that the study investigators deem would be detrimental for the patient to continue on the study
- If the patient desires to leave the study
- Patient starts taking other lipid lowering drugs including fibric acid derivatives, bile acid sequestrants and niacin preparations
- Patients will be dropped from the study if their CD4 count drops by fifty percent on two successive determinations, or falls below 250 cells/ μ l in the absence of any documented ongoing infections/inflammatory processes while on study

If subjects are discontinued from the study secondary to any of the above given reasons they will be replaced according to the prior randomization.

CLINICAL AND LABORATORY EVALUATION

Evaluation*	Screening	Randomization	D7 W1	D14 W2	D42 W6	D56 W8	D84† W12	D91 W13	D98 W14	D126 W18	D140 † W20	D168 W24
Documentation of HIV	Pos ELISA and Confirmatory Blot, previous results will be allowed											
Medical /Medication history	✓	✓	✓	✓	✓	✓	✓	✓	✓	✓	✓	✓
Nadir CD4	✓											
Clinical Assessment	✓	✓	✓	✓	✓	✓	✓	✓	✓	✓	✓	✓
Questionnaires		✓				✓	✓				✓	✓
Physical Exam	✓	✓				✓	✓				✓	✓
Hepatitis profile	✓											
Fasting lipid profile	✓	✓	✓			✓	✓	✓			✓	✓
Markers of inflammation		✓	✓			✓	✓	✓			✓	✓
Hematology	✓	✓		✓	✓	✓	✓		✓	✓	✓	✓
Chemistry including CK	✓	✓		✓	✓	✓	✓		✓	✓	✓	✓
Liver Function Tests	✓	✓		✓	✓	✓	✓		✓	✓	✓	✓
Urinalysis	✓	✓				✓	✓				✓	
Pregnancy Testing	✓	✓	✓	✓	✓	✓	✓	✓	✓	✓	✓	✓
Full FACs	✓	✓	✓			✓	✓	✓			✓	✓
HIV viral load (bdna)	✓ (3 viral load measures will be used to establish baseline)	✓	✓	✓	✓	✓	✓	✓	✓	✓	✓	✓
Statin/placebo		✓	✓	✓	✓	✓	✓	✓	✓	✓	✓	
Stored Plasma/PBMC		✓	✓	✓	✓	✓	✓	✓	✓	✓	✓	✓
Stored Sera		✓				✓	✓				✓	

- * Study consent will be signed at NNMC prior to screening and at randomization at the NIH
- † In the event subject is vaccinated these visits will be extended by 2 weeks

Table 1- Schedule of events

5.5 Breaking the blind

In the event of a medical emergency or in the event an off study criterion is met where knowledge of the treatment will affect medical management, the investigators after consulting with the medical monitor can break the blind. To break the blind investigators will contact the pharmacy department by pager and via electronic mail, as they will hold the randomization code.

In the rare event of such an occurrence the process will be documented in writing. If the DSMB decides to terminate the study, the blind will be broken and study participants and their primary physicians will be informed of their drug assignments.

5.6 Criteria for Stopping Enrollment

Once patient enrollment is completed the study will be closed for further enrollment or if the DSMB decides to terminate the study prior to complete enrollment. The DSMB will meet after half the participants in the clinical trial have completed the study. Alternatively they will also convene if two study patients have grade III or higher adverse events that in the opinion of the investigator are definitely, possibly or probably associated with the drug. Please note: unlike other lab AE's that would necessitate convening a DSMB if 2 subjects have a grade 3 or higher adverse event, the DSMB would convene only if the grade 3 CPK elevations are persistent.

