8.1.2 Reporting

All adverse events regardless of treatment group or relationship to the drug will need to be reported to the necessary IRB as per their requirements. As reporting requirements are somewhat different at NIAID and NNMC we will follow reporting requirements at both institutions.

All SAE will be reported within 24 hours of when the investigator learns of this event. to both the NIAID and the NNMC IRB. In addition to the above listed event any event that in the investigators judgment is serious even if it does not meet the above criteria will be reported as such.

Adverse events will be graded as per the attached toxicity table in Appendix 1. For toxicities not listed in the table, grading will be based on the schema provided below

- Grade 1: Transient or mild discomfort; no limitation in activity; no medical intervention/therapy required.

- Grade 2: Mild to moderate limitation in activity - some assistance may be needed; no or minimal medical intervention/therapy required.
- Grade 3: Marked limitation in activity, some assistance usually required; medical intervention/therapy required hospitalization possible.
- Grade 4: Extreme limitation in activity, significant assistance required; significant medical intervention/therapy required hospitalization or hospice care.

Adverse events will also be assessed for their relation to study medications and procedures.

Patients coming to the NIH clinical center often travel long distances and are hospitalized for procedures that are routinely done as outpatients at other hospitals. Such elective hospitalizations will not be reported as a SAE or an AE.

For all AEs, the clinician who examines and evaluates the subject will determine the adverse event's causality based upon the temporal relationship to administration of the study agent, the pharmacology of the study agent, and his/her clinical judgment. Terms to describe the degree of causality between the study agent and an event will be definitely, probably, possibly, unlikely related or not related. The best estimate at the time of reporting of the causal relationship between the experimental intervention and an adverse event and the degree of certainty about causality will be graded as follows:

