As the study is being done at both the NIAID and at the NNMC reporting requirements for both sites will be followed these include reporting all SAE within 24 hours after becoming aware of a subject death or a potentially life threatening serious adverse event. This will meet the reporting requirements of both the NIAID and the NNMC IRB, as the NIAID requires reporting within 7 days and the NNMC requires reporting within 24 hours of knowledge of death or potentially life threatening SAE. A completed NIAID IRB serious adverse event report will be submitted to the NIAID IRB within 15 days after becoming aware of an inpatient hospitalization (other than elective), a persistent or significant disability/incapacity, or a congenital anomaly/birth defect. Investigators will report within 15 days any other event or condition regardless of grade, which in their judgment represents an event reportable to the IRB. All other serious adverse events will be reported to the NIAID IRB at the time of the annual review. In addition a summary of all adverse events will be reported to the NIAID IRB with submission of a request for continuing review.

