8.2 Protocol monitoring and DSMB

Day to day protocol management will be provided by the PI at the NIH and by the sponsors of the study at NNMC. As this is a randomized placebo controlled trial, a DSMB will monitor the progress of the trial. The DSMB will be constituted through the NIAID. The DSMB will evaluate data after enrollment and completion of study by 50% of the study patients.

The trial will be conducted in compliance with this protocol, International Conference on Harmonization Good Clinical Practices (ICH/GCP) and all applicable regulatory requirements. Monitors under contract to the NIAID will visit the clinical research site(s) to monitor all aspects of the study in accordance with the appropriate regulations. The objectives of a monitoring visit will be: 1) to verify the prompt reporting of all data points, including reporting SAEs, checking availability of signed informed consents; 2) to compare individual subject records and the source documents (supporting data, laboratory specimen records and medical records to include physician progress notes, nurse' notes, subjects' hospital charts); 3) to ensure protection of study subjects, compliance with the protocol, and accuracy and completeness of records. The monitors also will inspect the clinical site regulatory files to ensure that regulatory requirements are being followed. During the monitoring visits, the investigator (and/or designee) and other study personnel will be available to discuss the study progress and monitoring visit findings. The investigator (and/or designee) will make study documents (e.g., consent forms) and pertinent hospital, CRFs or clinical records readily available for inspection by the local IRB, the site monitors, and the NIAID staff for confirmation of the study data

8.3 Data and Safety Monitoring Plan.

Day to day protocol management will be provided by the PI at the NIH and by the sponsors of the study at NNMC. As this is a randomized placebo controlled trial, a DSMB will monitor the progress of the trial. The DSMB will be constituted through NIAID. The DSMB will evaluate data after 50% of the study patients have completed study.

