9.4 Study Discontinuation

The study may be discontinued at any time by the IRB, the NIAID, the FDA, or other government agencies as part of their duties to ensure that research subjects are protected

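### The protocol provides no DSMB notice or meeting after a single drug-related death or life-threatening event; its only event trigger needs two patients

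*Combined protocol and SAP*

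**What the plan says.** Section 5.6 fixes one routine meeting: "The DSMB will meet after half the participants in the clinical trial have completed the study". Section 8.3 repeats it ("The DSMB will evaluate data after 50% of the study patients have completed study"), and section 8.2 says the same in slightly different words. Neither 8.2 nor 8.3 adds an event trigger or a route for serious adverse events (SAEs) to reach the board.

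The only event-driven meeting is in 5.6: "Alternatively they will also convene if two study patients have grade III or higher adverse events". The events must be rated by the investigator as definitely, possibly or probably associated with the drug. A further sentence narrows this rule by counting grade 3 CPK elevations only when they persist. Section 5.6 also recognises that the DSMB may terminate the study.

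On reporting, section 8.1.2 states "All SAE will be reported within 24 hours of when the investigator learns of this event" and names the NIAID and NNMC IRBs as recipients. It later reconciles the two IRBs' deadlines by "reporting all SAE within 24 hours after becoming aware of a subject death or a potentially life threatening serious adverse event". The DSMB is not mentioned there.

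Several provisions do respond to one event:
- Section 5.4 allows a patient with an SAE to be discontinued, involves the medical monitor in decisions to stop study drug, and for certain CPK findings requires "a conference call with representatives from all three participating sites".
- Section 5.5 says "the investigators after consulting with the medical monitor can break the blind" in an emergency.
- Section 9.4 says "The study may be discontinued at any time by the IRB, the NIAID, the FDA" or other government agencies.

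**The concern.** The event trigger counts patients and makes no distinction above grade III. Two patients with related grade 3 laboratory abnormalities convene the DSMB; one patient who dies of a related event does not. Under section 5.4 that patient's place is then filled under the prior randomization, and nothing requires the DSMB to look first.

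At stake is whether the board set up to monitor the trial learns promptly of the most serious kind of safety signal. The protocol itself says in 9.2.2 that little is known about temporary cholesterol lowering in normocholesterolemic HIV-positive patients. It uses 80 mg, the dose with the highest transaminase rate listed in 9.2.1 (2.3%). The primary comparison and its power are not affected.

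**Working it through.** The protocol states no figure to reproduce here. The check is a reading of every DSMB and SAE provision, plus simple arithmetic on timing.

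**1. What one related death or life-threatening event sets in motion**

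| Provision | Acts on one event? | Requires DSMB notice or review? |
|---|---|---|
| 5.6 event trigger | No, needs two patients | Yes, once the second qualifies |
| 5.6, 8.2, 8.3 halfway meeting | Only if the event came before it | Yes, at that meeting |
| 8.1.2 24-hour report | Yes | No, goes to the two IRBs |
| 5.4 discontinuation, medical monitor, CPK call | Yes | No |
| 5.5 unblinding | Yes | No |
| 9.4 study discontinuation | Yes, at discretion | No |

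No row both acts promptly on a single event and involves the DSMB.

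**2. Minimum wait for the scheduled meeting**

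Inputs: the last visit is day 168 (5.3.4 and Table 1), and the final visit has a 1-week window (5.3.5). No patient finishes before day 168 on schedule, so the halfway meeting falls at least 168 days after the first randomization. For an event on study day d of the first patient, the minimum wait is 168 − d:
- d = 7: 168 − 7 = 161 days (23 weeks)
- d = 56: 168 − 56 = 112 days (16 weeks)

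If final visits are a week early, these become 154 and 105 days. They are lower bounds for the first patient, because 11 patients must finish. Patients enrolled later can wait less. Accrual is not given, so the number of patients dosed during the wait cannot be stated.

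**3. After the halfway meeting**

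With 22 planned, 22 − 11 = 11 patients have not completed when the meeting becomes due. Whatever happens to them afterwards has no further planned DSMB meeting unless the two-patient count is reached.

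**4. How likely is such an event?**

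The documents allow one rough figure, for rhabdomyolysis only. Sections 6.1 and 9.2.2 report 5 cases in a trial of 10,001 coronary patients with median follow-up of 4.9 years:
- Rate: 5 / (10,001 × 4.9) = 0.000102 per person-year
- Atorvastatin exposure here: 22 × 8 weeks = 176 weeks, or 3.37 person-years
- Expected cases: 0.000102 × 3.37 = 0.00034

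This comes from another population, pools 10 and 80 mg, and covers one event type. It shows rarity but does not measure the frequency of all events that would count.

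**5. What a two-patient count misses**

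Let p be the chance that a patient has a qualifying event; the values used are assumptions, not from the documents. With 22 independent patients, P(at least one) = 1 − (1 − p)^22 and P(exactly one) = 22p(1 − p)^21.

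| Assumed p | P(at least one) | P(exactly one) | Share with only one |
|---|---|---|---|
| 1% | 19.8% | 17.8% | 17.8 / 19.8 = 90% |
| 5% | 67.6% | 37.5% | 37.5 / 67.6 = 55% |

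The rarer the events, the more often the first is also the only one, and the event trigger then never operates.

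**The case against.** The strongest reply concerns weight. Two IRBs hear within 24 hours, and three named bodies can halt the study at any time. The medical monitor takes part in every decision to stop study drug, and contracted monitors check that SAEs are reported promptly. What is missing is one more recipient. The drug is marketed, exposure is 8 weeks per patient, and liver tests and CK are checked repeatedly. The trigger was also thought about: it reaches down to possibly related events and has its own CPK rule. For 22 patients the threshold is partly a matter of judgement. The two-patient count also runs throughout, so an early first event still counts towards it.

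Most of that stands as context, and it keeps this from being a serious defect. It does not fill the gap, because none of those safeguards puts a single event before the DSMB.

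Two narrower objections also have some force. Section 5.6 says when the board will convene; it does not forbid other meetings, and a separate charter could add a rule. The documents neither include nor cite one, so the finding is limited to what the protocol specifies. And the rhabdomyolysis figure is a poor proxy: investigators are blinded, so placebo-period events could also be judged possibly related. It is used here only to show rarity.

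**Conclusion.** The concern holds. The protocol specifies no DSMB notice or meeting for a single drug-related death or life-threatening event. Before the halfway meeting, the only planned review is that meeting, at least 161 days away for a day-7 event in the first patient. After it, none is planned unless a second patient qualifies.

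This is a gap in DSMB oversight, not a lack of all oversight, and the event is unlikely. The conclusion rests on the protocol text and on no unseen charter providing otherwise. The waits assume the scheduled day-168 completion (a week less with the window). The change is worth making because it costs so little.

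**What to change.** Make two additions:
- In 8.1.2, send the existing 24-hour report of any death or potentially life-threatening SAE to the DSMB at the same time as to the two IRBs.
- In 5.6, state that one such event judged definitely, probably or possibly related to study drug convenes the DSMB, alongside the current two-patient trigger.

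The cost is two sentences, one more recipient on a report already being written, and an occasional ad hoc call of a board that already exists. Sample size, power, blinding and the visit schedule do not change.

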Myalgia and rhabdomyolysis have been reported with atorvastatin use. In the ASCOT study there was a single case of non-fatal rhabdomyolysis among 5168 patients randomized to atorvastatin. [40] In a study of secondary prevention of CAD, among 10,000 patients randomized to receive either 10 or 80 mg of atorvastatin there were 5 cases of rhabdomyolysis.[39] While rhabdomyolysis is a complication of atorvastatin it appears relatively rare.

The risk of myopathy is increased when atorvastatin is used in conjunction with azole antifungals, erythromycin, clarithromycin, niacin, fibric acid derivatives or cyclosporine [37]. Patients who use fibric acid derivatives, niacin and cyclosporine will not be enrolled into the

study. Patients who start azoles or erythromycin or clarithromycin while on study will be monitored closely for signs and symptoms of myopathy, patients on these drugs at the time of enrollment will not be eligible for this study until completion of therapy with these agents.

In addition the risk of myopathy is increased with the concomitant use of grape fruit juice and atorvastatin. These interactions are mediated via the cytochrome p 450 system; grape fruit juice is an inhibitor of this system [41] While on study patient will be advised to avoid grape fruit juice and grape fruit.

To reduce risk to our study patients we will monitor liver function (LFT) and creatinine phosphokinase (CPK) at baseline and as indicated in the schedule of events. Patients will also be questioned about myalgia or weakness at each visit. Presence of any of these symptoms will require complete evaluation as judged suitable by their health care provider. Patients who participate in this study will be asked to refrain from vigorous exercise regimens for the study period. Vigorous exercise is known to increase CPK levels and may cause patients to be unnecessarily excluded /withdrawn from the study.

- Pregnancy and breast feeding are contraindications for atorvastatin use; atorvastatin is classified as a pregnancy category X drug. Pregnant or nursing women will not be enrolled in this study and patients will be required to use reliable methods of contraception to be enrolled in this study. If a patient becomes pregnant on study, she will be asked to stop taking study drug and will be followed through her pregnancy and the peripartum period.

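### Section 5.6 counts a grade 3 CPK rise toward the two-patient DSMB trigger only if it is persistent, so a related rise that falls after an early drug stop can go uncounted

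*Combined protocol and SAP*

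**What the plan says.** Section 5.6 gives the DSMB two occasions to meet. One is scheduled: "The DSMB will meet after half the participants in the clinical trial have completed the study". The other is unscheduled: "they will also convene if two study patients have grade III or higher adverse events" that the investigator considers definitely, possibly or probably related to drug. Section 5.6 then sets CPK apart from other laboratory events: "the DSMB would convene only if the grade 3 CPK elevations are persistent". It does not say what persistent means.

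Section 5.4 does, for a different purpose (when to stop study drug). A CPK above 10 times the upper limit of normal, which 5.4 equates with grade 3 or higher, is repeated "within 1-3 days of the initial result and also at day 7". Drug is stopped for persistent elevation, meaning "CPK measurements that remain at the same level or are higher than the initial value, on three consecutive determinations", despite stopping exercise.

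Section 5.4 also lets drug be stopped before persistence is shown. CPK rises with grade 3 or higher symptoms, and significant symptoms or CPK rises outside the stated categories, go to a call among the three sites. Discontinuation is then decided case by case with the medical monitor. Separately, a subject may be discontinued if "Patient develops any condition that the study investigators deem would be detrimental for the patient to continue on the study".

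**The concern.** The count depends on what CPK does over about a week, and the decision to stop drug can change that. If the investigators stop drug promptly for a rise they think is drug-related, CPK is less likely to remain at or above its first value. The case may then fail the test that would have counted it. Section 8.1.2 points the other way on causality: it cites an event that lessens when drug is withdrawn (and returns on re-exposure) as the mark of a definite relation. Under 5.6 the fall on withdrawal takes the case out of the count.

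At stake is the only unscheduled DSMB trigger in the protocol, for a muscle toxicity that Sections 6.1 and 9.2.1 name as a hazard of this drug. Section 5.4 replaces discontinued subjects, so further patients could be enrolled before the DSMB has looked at the cases together.

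**Working it through.** **Which cases escape.** The two sections give this result for a CPK rise judged related:

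| Case | Counted under 5.6? |
|---|---|
| Grade 3 CPK, at or above the initial value at days 1-3 and day 7, on or off drug | Yes |
| Any CPK rise with related symptoms of grade 3 or higher | Yes, through the symptoms |
| Grade 4 CPK | Read literally, yes: the exception names grade 3 only |
| Grade 3 CPK, symptoms below grade 3, drug stopped early, CPK falls but stays above 10 times the upper limit | No by the 5.4 definition; arguably yes by the ordinary meaning of persistent |
| Same, but CPK falls below 10 times the upper limit | No on either reading |

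This takes the three determinations in 5.4 to be the initial value and the two repeats. Two patients in the last row contribute 0 of the 2 events needed.

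**How long until the scheduled look.** In Table 1 the first on-treatment CK is at day 14 and the last visit is day 168. Half of 22 is 11 patients. If both cases appear at day 14 and the 11 patients who make up the half all start on the same day as they do (an assumption), the wait is 168 − 14 = 154 days, or 22 weeks. Staggered enrolment could lengthen or shorten it, so this is an illustration and neither an expected value nor a bound.

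**How likely.** The documents give no rate of CPK events. Let p be the assumed per-patient risk of the whole scenario (related, grade 3 CPK, symptoms below grade 3, early stop, later fall) and n the number of patients:

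P(2 or more) = 1 − (1 − p)^n − n·p·(1 − p)^(n−1)

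For p = 0.01 and n = 22: 1 − 0.8016 − 0.1781 = 0.020.

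| Assumed p | n = 22 | n = 11 |
|---|---|---|
| 0.1% | 0.02% | 0.005% |
| 0.5% | 0.5% | 0.13% |
| 1% | 2.0% | 0.5% |
| 2% | 7.1% | 2.0% |

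The n = 11 column is relevant because the harm is review missed before the half-way look. The number exposed by then is not known, but lies between about 11 and 22 if replacements are ignored. With n = 22, the probability reaches 1% only at p of about 0.69%, and 5% only at about 1.64%.

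The nearest rates in the documents are for rhabdomyolysis (Section 6.1): 1 in 5168, and 5 in about 10,000. With n = 22 these give about 0.0009% and 0.006%. Rhabdomyolysis is a different and rarer event, so they are indicative only.

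**The case against.** **The exemption is deliberate.** Section 5.6 flags it openly, and Section 6.1 supplies a related reason: "Vigorous exercise is known to increase CPK levels and may cause patients to be unnecessarily excluded" or withdrawn. This stands as a reason for exempting transient exercise rises. It does not reach a rise judged drug-related and serious enough to stop drug.

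**Possibly related is a low bar.** By the definition in 8.1.2, a possibly related event can be explained equally well by other causes. A blinded patient with an exercise rise, even on placebo, could be graded this way and stopped as a precaution. Counting drug stops would bring that case in. This stands, and is a real cost of the fix.

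**The 5.4 definition is borrowed.** It was written for stopping drug, and applying it to 5.6 is an inference. This also stands, and it narrows the certain gap to falls below 10 times the upper limit of normal.

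**Other safeguards exist.** Section 8.1.2 sends all adverse events to the IRBs as they require, and for serious ones "All SAE will be reported within 24 hours of when the investigator learns of this event". The three-site call could let the same group see both cases. Section 9.4 lets the IRB, NIAID or FDA stop the study. All true, but none of these provisions sends the cases to the DSMB.

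**The route is limited.** Under 5.4 an asymptomatic grade 3 rise is retested; stopping drug at once is not the default. The documents give no time course for CPK after stopping, so the expected fall is plausible but unquantified.

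**Conclusion.** The gap is real but narrow, and closing it is a cheap improvement to consider, not the correction of an error. As written, two patients taken off drug for related grade 3 CPK rises need not bring the DSMB together if their symptoms were below grade 3 and their CPK then fell.

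Three stronger readings are not supported. A reader might infer that stopping drug by itself disqualifies a case. It does not: persistence depends on CPK values, and a rise that stays up off drug still counts. A reader might infer that patients with such rises are unprotected. They are not: the call, the medical monitor, investigator discretion and IRB reporting all act on the individual, and only unscheduled review across patients can be missed. A reader might take the percentages above as estimates of risk in this trial. They follow from assumed values of p.

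The conclusion rests on reading persistent in 5.6 either as 5.4 defines it or in its ordinary sense. Symptom grading relies on Appendix 1, which is not in the text available for this review.

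**What to change.** In Section 5.6, count a grade 3 or higher CPK rise judged definitely, probably or possibly related if either (a) it is persistent as defined in Section 5.4, or (b) study drug was discontinued because of it. This supplies the missing definition and leaves the decision to stop drug where it is, with the three-site call and the medical monitor.

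The cost is one clause and no new visits or tests. The exercise exemption is kept for transient rises for which drug is not stopped. It is not kept in full: an exercise rise graded possibly related, with a precautionary stop, would now count, so an extra DSMB meeting may occasionally follow. The clause would not reach a non-persistent rise first found at the end of a treatment period (day 56 or day 140), because drug then ends on schedule and is not stopped on account of the rise.
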